We will use ultra-high resolution diffusion spectrum imaging (DSI) to map the structural connectome and identify brain regions with high and low regional controllability. We will directly test whether TMS targeted to control points using network control theory on a single-subject basis results in greater network responses in single-pulse TMS/fMRI recordings. Specifically, we will vary the stimulation target in a counterbalanced order across two days of TMS/fMRI, where stimulation of a prefrontal control point (with high regional controllability) is compared with stimulation of a prefrontal region with low regional controllability. During each of these TMS/fMRI sessions, we will also evaluate the impact of functional context by stimulating under counterbalanced conditions of high or low working memory load. Critically, following these initial single-pulse experiments that interrogate network activation and interaction, each participant will receive rTMS in the scanner to modulate the system. We expect that rTMS targeted with network control theory and given immediately following high working memory load (a warm functional context) will produce greater improvements in working memory performance. As an exploratory component, a subset of these experiments will be repeated in a sample of young adults with ADHD and documented executive dysfunction. As working memory dysfunction is a common and debilitating feature of many neuropsychiatric illnesses, these data will provide evidence of the potential clinical impact of next-generation personalized neuromodulatory therapies.

Primary outcome variable(s)

Brain network responses to single pulse TMS to prefrontal area with high regional controllability versus low regional controllability. Working memory performance pre- versus post-rTMS to a TMS target with high regional controllability versus a TMS target with low regional controllability.

Secondary outcome variable(s)

Brain network response to single pulse TMS in the context of high working memory load versus low working memory load. Working memory performance in patients with ADHD after rTMS to a high regional controllability point.

Background

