performance in both clinical and non-clinical samples (O'Reardon et al., 2007; Brunoni & Vanderhasselt, 2014). The majority of neuroscientific studies seeking to understand brain responses to TMS ignore that the brain can be in many different states when stimulation is delivered; however, brain state is naturally modulated by the functional context of experiments based on their cognitive demands. Recent efforts measuring and controlling context have underscored the impact of functional context on TMS-induced changes in behavior (Bassett et al., 2011; Calhoun, Miller, Pearson, & Adal, 2014). Notably, previous work from our group and others has shown that visualizing a motor response potentiates evoked responses to TMS stimulation to the motor cortex ([name], Bruce, & Nitschke, 2008; Sparing et al., 2002). As such, we infer that applying TMS at a particular moment during a cognitive task may allow us to manipulate the interaction between brain state and the effects of TMS on brain networks. Specifically, we hypothesize that stimulation within a specific functional context will enhance network responses to TMS as well as its impact on behavior, in particular working memory. In addition to manipulating specific functional contexts of stimulation to enhance the impact of TMS on behavior, we also aim to explore the effect of specific stimulation sites on brain responses to TMS. Decades of cognitive neuroscience research have established a well-defined network of brain regions that are essential for WM and executive processes, including regions within the fronto-parietal network (FPN), such as the dorsolateral prefrontal cortex (DLPFC) and the superior parietal cortex (Wager & Smith, 2003; Rottschy et al., 2012; Owen, McMillan, Laird, & Bullmore, 2005). Furthermore, recent work from our group has demonstrated that accurate WM performance also depends on deactivation of regions within the default mode network (DMN) including the ventromedial prefrontal cortex and the posterior cingulate, and reduced functional connectivity between the FPN and the DMN (Satterthwaite et al., 2013). As in previous work, we call this constellation of activity and connectivity functional network segregation (Satterthwaite et al., 2013; Baum et al., 2017). Critically, earlier work by PI [name] using TMS/fMRI has established that TMS can induce this same pattern of FPN activation and DMN deactivation (Chen et al., 2013). Thus, there is evidence of concordance between the brain circuits required for WM function and the brain circuits influenced using our TMS protocols. We hypothesize that stimulation during a WM task that instantiates this functional context will enhance both brain and behavioral responses to TMS. While our preliminary data guides our focus on WM, we anticipate that the interaction between functional context and stimulation may be a general mechanism of TMS response that could be extended to other brain networks and cognitive systems in future. Moreover, this study explores how we may be able to maximize the downstream brain network effects of TMS based on specific stimulation site. Specifically, we look at applying the network control theory to individualized TMS targeting. The network control theory (NCT) suggests that alterations in the activation of a single node in a brain network can lead to distributed and system-wide effects whose exact pattern depends on the structure of the network interconnecting all nodes (Liu, Slotine, & Barabasi, 2011; Muldoon et al., 2016). Originally developed in the field of systems engineering, NCT provides a framework for understanding how key nodes, or control points, can exert disproportionate influence over system function (Liu et al., 2011). NCT is applicable in systems that are controlled through signals that originate at the control point and move through the network. This description is identical to the rationale for administering repetitive TMS to a specific brain area and expecting widespread effects on brain and behavior. Despite such widespread use in disparate fields and evident similarity to our understanding of how TMS influences human behavior, there has not yet been research exploring TMS in the context of network control theory (NCT). Efforts to test such a theory are critical, as validation could provide a generalizable mechanism of TMS that would prove essential for choosing the target of stimulation, titrating stimulation dose, and personalizing stimulation to the subjects intrinsic brain network architecture. In a sample of healthy adults we will use ultra-high resolution diffusion imaging (DSI) to map the structural connectome and identify brain regions with high and low regional controllability. We will directly test whether TMS targeted to control points using NCT on a single-subject basis results in greater network responses in single-pulse TMS/fMRI recordings. Specifically, we will vary the stimulation target in a counterbalanced order across two days of TMS/fMRI, where stimulation of a prefrontal control point (with high regional controllability) is compared with stimulation of a prefrontal region with low regional controllability. During each of these TMS/fMRI sessions, we will also evaluate the impact of functional context by stimulating under counterbalanced conditions of high or low WM load. Critically, following these initial single-pulse experiments that interrogate network activation and interaction, each participant will receive rTMS in the scanner to modulate the system. We expect that rTMS targeted with NCT and given immediately following high WM load (a warm functional context) will produce greater improvements in WM performance. Furthermore, we predict that these behavioral changes will be mediated by functional network segregation. Importantly, a subset of these experiments will be repeated in a sample of young adults with ADHD and documented executive dysfunction. As WM dysfunction is a common and

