
debilitating feature of many neuropsychiatric illnesses (including ADHD, psychosis, and mood disorders), these data will provide evidence of the potential clinical impact of next-generation personalized neuromodulatory therapies (Shanmugan et al.,2016).

Study Design

Phase*

Not applicable

Design

We will use a 2x2x2 factorial design to probe the impact of network control theory guided targeting and functional context using single pulse TMS/fMRI. Within-session changes in working memory performance and network responses following neuromodulation with rTMS will be evaluated in healthy adults and in patients with ADHD. Healthy young adults will undergo four neuroimaging sessions. Following medical, clinical, and cognitive assessment, neuroimaging session one will consist of ultra-high resolution diffusion spectrum imaging to map the structural connectome and identify control points. This initial session will be followed by two TMS/fMRI sessions which combine experiments that interrogate circuits with single-pulse TMS/fMRI as well as rTMS to modulate circuits. The two TMS/fMRI sessions will compare brain responses to stimulation targeted on the basis of high versus low regional controllability. Target location will alternate across neuroimaging sessions two and three in a counterbalanced fashion to test our hypotheses. For each of these two TMS/fMRI sessions, stimulation will occur within a counterbalanced functional context of high versus low working memory load. Within each TMS/fMRI session, initial interrogation using single-pulse stimulation will be followed by neuromodulatory rTMS. Single-pulse stimulation that was conducted pre-TMS will be repeated after neuromodulation, in order to evaluate the effect of network control theory targeting and the functional context of recent working memory load (warm rTMS) on working memory performance and network segregation. We will also study 35 patients with ADHD and working memory deficits. In two scanning sessions, we will first identify control points and then record responses to network control theory-guided rTMS administered during a functional context of high working memory load. Subjects can also complete an optional task while they undergo an fMRI scan if the task is available.

Study duration

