
The following documents are currently attached to this item:

There are no documents attached for this item.

Deception

Does your project use deception?

No

International Research

Are you conducting research outside of the United States?

No

Analysis Plan

For the primary within-subjects analyses, a time (pre vs post rTMS) by working memory load (high vs low) by stimulation site (high vs low controllability) ANOVA will be done both on working memory performance (d prime sensitivity) as well as fMRI voxelwise brain responses. In addition, the group level factor (ADHD or Healthy) will be added to the same model for a separate mixed-effects ANOVA.

The following documents are currently attached to this item:

There are no documents attached for this item.

Data confidentiality

- x Paper-based records will be kept in a secure location and only be accessible to personnel involved in the study.
- x Computer-based files will only be made available to personnel involved in the study through the use of access privileges and passwords.
Prior to access to any study-related information, personnel will be required to sign statements agreeing to protect the security and confidentiality of identifiable information.
- x Wherever feasible, identifiers will be removed from study-related information.
A Certificate of Confidentiality will be obtained, because the research could place the subject at risk of criminal or civil liability or cause damage to the subject's financial standing, employability, or liability.
- x A waiver of documentation of consent is being requested, because the only link between the subject and the study would be the consent document and the primary risk is a breach of confidentiality. (This is not an option for FDA-regulated research.)
- x Precautions are in place to ensure the data is secure by using passwords and encryption, because the research involves web-based surveys.
Audio and/or video recordings will be transcribed and then destroyed to eliminate audible identification of subjects.

Subject Confidentiality

Patients entering the study will be given a unique identifying code. This code will be used on all data obtained from scans or the medical record. Only one password protected document connecting the code with the participant name will exist. Everything will be immediately coded and this coded information will be stored in secure cabinets inside locked rooms or in password protected, IRB compliant online databases, such as REDCap.

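### Does the Analysis Plan need a network-segregation score and a mediation test because the Background and Design sections mention them?

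*Combined protocol and SAP*

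**What the plan says.** The Analysis Plan section is two sentences long. The first crosses time (before and after rTMS), memory load and stimulation site for the main within-participant comparisons, and says that this "ANOVA will be done both on working memory performance (d prime sensitivity) as well as fMRI voxelwise brain responses". The second says that "the group level factor (ADHD or Healthy) will be added to the same model for a separate mixed-effects ANOVA". It does not mention connectivity, a segregation score, mediation, regions of interest or a voxelwise threshold.

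Three other sections go further:

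- **Background.** It links good working memory to frontoparietal (FPN) activity, to deactivation of the default mode network (DMN), and to "reduced functional connectivity between the FPN and the DMN". It then says "we call this constellation of activity and connectivity functional network segregation", and later adds "we predict that these behavioral changes will be mediated by functional network segregation".
- **Design.** The single-pulse run is repeated after rTMS to evaluate targeting and "the functional context of recent working memory load (warm rTMS) on working memory performance and network segregation".
- **Overall objectives.** This section speaks of "initial single-pulse experiments that interrogate network activation and interaction".

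The outcome lists are narrower. The primary brain outcome is "Brain network responses to single pulse TMS to prefrontal area with high regional controllability versus low regional controllability". The primary behavioural outcome is the change in working memory across rTMS, compared between the two targets. The secondary outcomes are the single-pulse response by memory load, and working memory in ADHD participants after rTMS at the high-controllability point. Segregation and mediation are in neither list.

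**The concern.** A stated purpose of the repeat run and a stated prediction appear to have no analysis. Segregation is defined partly by coupling between two networks, and an ANOVA on response amplitude at each voxel does not estimate coupling. Mediation is a claim about individuals: those whose networks changed more should also have improved more. Two separate ANOVAs, one on brain response and one on d prime, can both be positive without that being so.

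If the trial later claimed a mechanism from the two ANOVAs alone, the claim would be unsupported. If a segregation measure were devised once the data were in hand, it could be chosen to suit the result. The same worry extends to the primary brain outcome, because the Analysis Plan does not say which term tests it, which runs and signal feed it, or how the voxelwise map is corrected.

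**Working it through.** The documents give no alpha, power, effect size or standard deviation, so there is no stated figure to reproduce. The check compares the sections and adds illustrations on assumed values.

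**1. Does each listed outcome have a test?** A 2×2×2 model has 2³ − 1 = 7 effects. Four contain site.

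| Listed outcome (healthy participants) | Measure | Term in the planned model |
|---|---|---|
| Primary, brain | single-pulse response | site |
| Primary, behaviour | d prime | site × time |
| Secondary, brain | single-pulse response | load |

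All three are present. The ADHD outcome belongs to the group model and is not at issue here.

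**2. How open is the primary brain term?** If all four site terms were rival tests at an assumed 0.05 and independent, the chance of at least one false positive would be 1 − 0.95⁴ = 18.5%. The outcome list does not leave four candidates, however. It names the comparison between sites, and site × time is the behavioural outcome's comparison. Two legitimate readings remain: site over both runs, or site in the run before rTMS. If both were tried and the better one reported, independence would give 1 − 0.95² = 9.75%. The true figure would be lower, because both use the pre-rTMS run.

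**3. Which parts of segregation does the plan reach?** A voxelwise response map covers FPN activation and DMN deactivation. Amplitude alone does not cover coupling: two simulated regions with mean responses +1 and −1 had the same means whether their correlation was +0.5 or −0.5. But the Analysis Plan does not say that the response is amplitude. The same factors can be applied voxel by voxel to seed-connectivity maps. No combined score and no participant-level link to d prime is specified.

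**4. Would two ANOVAs stand in for mediation?** Assume n = 40 (Target population section), one segregation score per run, a site × time effect of 0.5 SD on both measures, two-sided 0.05, and r as the correlation between the two site-by-time differences.

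- Each ANOVA term has power 0.869 (noncentral t, 39 df).
- With r = 0, both are significant in 0.869² ≈ 76% of trials. Simulation gives 77%, 78% and 79% at r = 0.3, 0.4 and 0.5.
- A joint-significance mediation test with r = 0 rejects in 0.869 × 0.05 = 4.3% of trials.
- With r > 0, by normal approximation, the first path has power Φ(0.5√40 − 1.96) = 0.885. The second has power Φ(atanh(r)·√36 − 1.96) = 0.459, 0.720 and 0.909. The products are about 41%, 64% and 80%.
- Over effects of 0.3 to 0.6 SD and r of 0.3 to 0.5, the product runs from 22% to 88%.

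The pair of ANOVAs therefore cannot distinguish mediation from its absence. That is true by logic, and the protocol nowhere proposes to use the pair in that way.

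**The case for a change.** The best case for a change is that segregation is more than background colour. The Design section gives it as a reason for repeating the run, and the objectives speak of interaction between networks as well as activation. The scans needed are already planned, so an exploratory score and model would cost only wording, and fixing the score in advance would prevent a convenient choice later. The primary brain outcome is a listed one, so leaving its term, runs and correction unwritten allows some latitude.

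Much of this is factually right. The Analysis Plan specifies no connectivity measure, no score and no mediation model, and two ANOVAs would not support a mediation claim.

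The step from there to a required change does not stand. The Analysis Plan introduces its model as the one for the primary within-participant comparisons, so its silence on an unlisted mechanism contradicts nothing. The primary brain comparison is named in the outcome list. The illustrated percentages rest on a score and effect sizes found nowhere in the documents, so they are not error rates of the planned analysis. The natural addition, mediation of the site effect, would also miss part of the prediction, which in the Background follows from targeting and recent high memory load together. The mediator is not randomised, so even a positive result would be open to other explanations.

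**Conclusion.** No change to the plan is needed. This is missing detail about a mechanism outside the outcome lists, together with analysis details that a competent imaging team settles in the ordinary way: which runs enter, which site term is read, and how the map is corrected. Run as written, the model gives a sound test of each listed brain and behavioural comparison in healthy participants, and no stated rule gives a wrong answer.

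A mediation model would gain little. At 40 participants its power is about 41% to 80% for 0.5 SD effects with r from 0.3 to 0.5, and 22% to 88% over the wider assumed range. Deleting the prediction would change no result.

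The conclusion assumes that any later statement about segregation or mediation is presented as exploratory and rests on its own analysis, not on two positive ANOVAs. It also assumes that the voxelwise map is corrected by an accepted method. The Background refers to a grant submission that is not available here; nothing above depends on what it contains.

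### The ADHD-versus-healthy model reuses a time × load × site design that the ADHD group fills only in part, and the plan leaves open whether the load before rTMS is modelled, matched or confounded with group

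*Combined protocol and SAP*

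**What the plan says.** All references are to the combined protocol and SAP.

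- **Primary model (Analysis Plan).** The within-subject analysis is "a time (pre vs post rTMS) by working memory load (high vs low) by stimulation site (high vs low controllability) ANOVA", applied to d prime and to voxelwise fMRI responses.
- **Group comparison (Analysis Plan).** "the group level factor (ADHD or Healthy) will be added to the same model for a separate mixed-effects ANOVA". Healthy data are not restricted to matched sessions, and no separate term for the context of rTMS is named.
- **ADHD condition (Study Design, Design).** Patients have two scanning sessions. In the second, the study will "record responses to network control theory-guided rTMS administered during a functional context of high working memory load". The secondary outcome is "Working memory performance in patients with ADHD after rTMS to a high regional controllability point", so the target is the high-controllability one. Under Procedures, the second TMS/fMRI visit is for non-symptomatic subjects only.
- **Healthy condition (Design).** Participants have two TMS/fMRI sessions with opposite targets, and "stimulation will occur within a counterbalanced functional context of high versus low working memory load". Single-pulse stimulation is repeated after rTMS to evaluate targeting and "the functional context of recent working memory load (warm rTMS) on working memory performance and network segregation".
- **Predicted direction (Overall objectives).** rTMS guided by network control theory and "given immediately following high working memory load (a warm functional context) will produce greater improvements in working memory performance".
- **Status (Overall objectives).** The ADHD work is labelled exploratory. The Accrual section nevertheless expects the sample to support a comparison of patients with non-disordered participants.

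**The concern.** The sentence on the group factor treats the two groups as if they went through the same design. They do not. The ADHD group has one target and one stated rTMS context. The healthy group has two targets and apparently two contexts. The site imbalance can be removed by using only the healthy high-controllability session. The context imbalance would remain, because some of those sessions may have had rTMS after low load while every ADHD session had it in a high-load context.

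The trial itself predicts that this context changes the working memory gain. If the prediction is right and context is not in the model, the healthy mean gain is diluted and the ADHD mean gain is not. The group × time term would then overstate the ADHD response relative to healthy participants, or hide a smaller one. If context is in the model, the difficulty is that several group terms have no ADHD data behind them.

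**Working it through.** The plan gives no alpha, power, effect size or SD for this comparison, so there is no stated figure to reproduce.

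**1. How many rTMS contexts can one session hold?** Procedures give iTBS as 2 s on and 8 s off, repeated 20 times: 20 × 10 s = 200 s = 3.3 min. The stated total of repetitive stimulation is about 4 min, and two runs would take 6.7 min, so there is one run per session. A healthy participant therefore has two rTMS runs, one per target, and can fill at most two of the four target × context combinations. This makes the scored task's load the more natural meaning of the within-subject load factor, but the text does not say so.

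**2. Can the same model be fitted?** Time × load × site × group with all interactions has 2⁴ = 16 coefficients. Taken together, healthy participants can fill 8 time × load × site cells.

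| Meaning of load | ADHD cells filled | Rank | Terms lost |
|---|---|---|---|
| Load of the scored task | 4 of 8 (high target only) | 12 of 16 | the 4 containing group × site |
| Context of rTMS | 2 of 8 (high target, high context) | 10 of 16 | those 4, plus group × load and group × load × time |

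Neither reading lets the full model be fitted. Under the second, a group effect averaged over load relies on empty ADHD cells.

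**3. What happens if context is unmodelled?** This is an illustration under the task-load reading only. Inputs from Target population: 40 usable healthy and 35 usable ADHD participants. Assumptions: high-controllability sessions only, half of the healthy ones low-context, within-session change with SD 1, no true group difference, two-sided 5% test, and a context effect c shown as a range.

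Bias = (low-context share) × c = 0.5c. Rejection rates are from 20,000 simulated trials per value of c, with a normal approximation alongside.

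| c (SD) | Bias (SD) | Rejection, unmatched (simulated) | Rejection, unmatched (approximation) | Rejection, matched on high context (simulated) |
|---|---|---|---|---|
| 0.3 | 0.15 | 9.4% | 9.9% | 4.9% |
| 0.5 | 0.25 | 17.6% | 18.7% | 4.9% |
| 0.8 | 0.40 | 36.5% | 38.5% | 4.5% |

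The share matters too. At c = 0.5, a low-context share of 25% gives about 8% and a share of 75% about 36%, by the approximation.

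**4. What does matching cost?**
- All 40 healthy against 35 ADHD: SE = √(1/40 + 1/35) = 0.231 SD.
- 20 matched healthy (assumption) against 35: SE = √(1/20 + 1/35) = 0.280 SD. The ratio is 1.21.
- The difference detectable with 80% power is (1.96 + 0.84) × SE, which goes from 0.65 to 0.79 SD.

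Keeping all 40 with a context term gives the same 0.280. All ADHD sessions are high-context, so the low-context healthy sessions inform only the context effect and the residual variance.

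**5. What does session order add?** ADHD patients have only a first TMS/fMRI session. Under counterbalancing, some healthy high-controllability sessions fall at Visit 4, after an earlier rTMS run and earlier N-back practice. Assume an even split of context and order, with 10 healthy participants per combination.
- Additive terms for context and order, read at high context and first session: the variance of the healthy prediction is 3/40, so SE = √(3/40 + 1/35) = 0.322 SD.
- Visit 3, high-context sessions only: SE = √(1/10 + 1/35) = 0.359 SD.

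**The case against.** The strongest reply is that low-load rTMS in healthy participants is inferred. Overall objectives and Background attach the counterbalanced load conditions to the single-pulse phase, with rTMS following. The secondary outcome on load also concerns single pulses. The rTMS paragraph in Procedures mentions no load context, only five minutes of fMRI before iTBS. This stands. A reader might infer that the healthy comparator certainly received a different rTMS condition, and the documents do not establish that. What supports variation is the Design aim of evaluating recent load before rTMS, which needs the load to vary, and only the healthy group could supply that.

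The second reply is that load in the ANOVA may already be the functional-context factor, since the Design section calls the study a 2×2×2 factorial probing targeting and functional context. This also stands as a possible reading. It replaces the silent bias with empty cells and inestimable group terms, so it does not rescue the sentence in the Analysis Plan.

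Third, the component is exploratory, the group model is separate, and the listed ADHD outcome names no healthy comparator. This limits the consequence. The group comparison is still written into the Analysis Plan and anticipated under Accrual.

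Finally, matching on context alone would leave session order unmatched. That is correct, and the fix covers it.

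**Conclusion.** The concern holds as a defect of specification in the exploratory group comparison. Each reading of the plan leaves something to correct:

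- **Load is the scored task's load:** rTMS context is unmodelled and, if healthy contexts vary, confounded with group.
- **Load is rTMS context:** the ADHD low-context cells are empty, and the averaged group and group × load effects cannot be estimated.
- **All healthy rTMS follows high load:** there is no context confounding, but the warm-rTMS evaluation promised in the Design section cannot be done.

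A reader might take the 10% to 36% range as the test's actual false-positive rate. It is not. It requires the task-load reading, a 50% low-context share, unit SD and a context effect of 0.3 to 0.8 SD, and the documents give none of these. Nor does the point reach the primary outcomes: the healthy within-subject analysis is unaffected by how group is added. Correction is advisable because the comparison is planned and the remedy is small.

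**What to change.** Do not add group to the full model. In the Analysis Plan:

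1. Define load as either the load of the scored task or the context of rTMS, and state which load preceded iTBS in healthy sessions. Overall objectives, Design, Procedures and Analysis Plan must be reconciled on this.
2. Define the exploratory ADHD-versus-healthy contrast as group × time, using only the healthy high-controllability session. Either restrict it to sessions where iTBS followed high load, or include pre-iTBS load context and its interaction with time and read the group effect at high context.
3. Adjust for healthy session order (Visit 3 or 4), or show a sensitivity analysis on Visit 3 sessions only.
4. State that healthy sessions with rTMS after low load, if any, are not a direct comparator for the ADHD group.

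This takes a few sentences and no new data, provided the load before iTBS is recorded for each session, which the documents do not confirm. The price is precision. If half of the 40 healthy sessions match, the standard error rises from 0.231 to 0.280 SD, about 21%. Dealing with order as well takes it to about 0.32 to 0.36 SD under the even split assumed above, so a Visit 3-only result is best kept as a sensitivity analysis.
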